12. STATISTICAL ANALYSES

12.1. Sample Size

Planned number of patients: 190 patients (95 in each group)

The sample size was determined based on the primary efficacy endpoint, OS.

Assuming that event incidence shows an exponential distribution, that median for sorafenib monotherapy OS is 10 months, and that adding hepatic arterial infusion chemotherapy improves median OS by 70% [28] (hazard ratio: 0.59 [combination therapy with HAIC versus sorafenib monotherapy]), 112 events would be necessary to achieve power of 80% for a one-sided α of 0.05 and 1:1 group assignment. The necessary number of events should be observed if 164 patients are followed over a study period of 36 months (enrollment period of 24 months and follow-up period of 12 months). Target enrollment was set at 190 patients (95 in each group) on the assumption that about 15% of patients will be unfollowable.

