0.6. Planned Enrollment and Study Period

Planned enrollment: 190 patients (95 in each group)
Enrollment period: 45 months (starting December 2010)
(to be completed in June 2014)
Overall study period: 57 months (to be completed in June 2015)

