2.6.5. Rationale for sample size

Planned number of patients: 190 patients (95 in each group)

The number of patients was determined based on the primary efficacy endpoint, OS.

If event incidence shows an exponential distribution, that median for sorafenib monotherapy OS is 10 months, and that adding hepatic arterial infusion chemotherapy improves median OS by 70% [28] (hazard ratio: 0.59 [combination therapy with HAIC versus sorafenib monotherapy]), then 112 events would be necessary to achieve a power of 80% for a one-sided α of 0.05 and 1:1 group assignment. The necessary number of events should be observed if 164 patients are followed over a study period of 36 months (enrollment period of 24 months and follow-up period of 12 months). Target enrollment was set at 190 patients (95 in each group) on the assumption that about 15% of patients will be unfollowable.

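### 112 events with 80% power do not match a one-sided alpha of 0.05: those inputs need 88–89 events, and 112 is the two-sided 0.05 figure

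*Protocol*

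**What the plan says.** The sample size argument appears twice in the Protocol with the same figures. Section 12.1 assumes exponential survival and a median of 10 months on sorafenib alone. It supposes that "adding hepatic arterial infusion chemotherapy improves median OS by 70"%, which it gives as a hazard ratio of 0.59, and concludes that "112 events would be necessary to achieve power of 80% for a one-sided α of 0.05 and 1:1 group assignment". Section 2.6.5 repeats this: "112 events would be necessary to achieve a power of 80% for a one-sided α of 0.05 and 1:1 group assignment".

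Both sections then say that 164 patients, with 24 months of enrollment and 12 of follow-up, should yield these events. The target is raised to 190 to allow for about 15% who cannot be followed.

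Section 11.1 names Kaplan-Meier estimation and the Cox model for overall survival but gives no test level or sidedness. Sections 11.1 and 12.4 rule out an interim efficacy analysis. The one-sided 0.05 in the sample size sections is therefore the only significance level the protocol attaches to the primary comparison.

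**The concern.** Given the hazard ratio and the allocation, the alpha, the power and the number of events are tied together: any two fix the third. The stated trio looks wrong because 112 is well above what one-sided 0.05 and 80% power require for so large an effect, and it coincides with the familiar two-sided 0.05 result.

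The success criterion for the primary endpoint is at stake. If the final test follows the words, superiority is claimed at a 5% one-sided error rate. If it follows the event count, the rate is 2.5% per side. Some observed hazard ratios would be positive under one reading and negative under the other. Section 2.3 says the trial is meant to establish the combination as standard therapy, so the criterion should not rest on a sentence that contradicts itself.

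**Working it through.** **Inputs (Protocol 2.6.5 and 12.1).** Medians of 10 and 17 months (10 × 1.7), so HR = 1/1.7 = 0.588, printed as 0.59; 1:1 allocation; power 80%; alpha 0.05, one-sided as stated; 112 events; 164 patients; 24 + 12 months.

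**Events required.** Schoenfeld: d = 4(z_alpha + z_power)² / (ln HR)². Freedman: d = (z_alpha + z_power)² × [(1 + HR)/(1 − HR)]².

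- One-sided 0.05, Schoenfeld, HR 1/1.7: 4(1.645 + 0.842)² / (0.5306)² = 87.8, so 88. At HR 0.59: 88.8, so 89.
- Two-sided 0.05, Schoenfeld, HR 1/1.7: 4(1.960 + 0.842)² / (0.5306)² = 111.5, so 112. At HR 0.59: 112.8, so 113.

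| Method | One-sided 0.05 | Two-sided 0.05 |
|---|---|---|
| Schoenfeld, HR 1/1.7 | 88 | **112** |
| Schoenfeld, HR 0.59 | 89 | 113 |
| Freedman, HR 1/1.7 | 92 | 117 |
| Freedman, HR 0.59 | 93 | 119 |
| Lachin-Foulkes, 24 + 12 months | about 91 | about 116 |

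The protocol's 112 is reproduced exactly by Schoenfeld with the unrounded hazard ratio at two-sided 0.05. No one-sided 0.05 entry exceeds 93. Rounding the hazard ratio moves the Schoenfeld result by one event, whereas the gap is 24 (112 − 88).

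**Power at 112 events.** Power = Φ(√(112/4) × |ln HR| − z_alpha). With HR 1/1.7, √28 × 0.5306 = 2.808.

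- One-sided 0.05: Φ(2.808 − 1.645) = 87.8% (87.4% at HR 0.59; Freedman 86.1–86.4%).
- Two-sided 0.05: Φ(2.808 − 1.960) = 80.2% (79.7% at HR 0.59).

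Conversely, 112 events and 80% power imply a one-sided alpha of 0.0246–0.0256 by Schoenfeld.

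**Could another stated feature explain the gap?** No alpha is spent, because there is no interim efficacy analysis. The 15% allowance is applied to patients, not to events. To check the patient number, assume uniform accrual over A months, F further months of follow-up, and hazard λ = ln 2 / median. The probability of death is then 1 − [e^(−λF) − e^(−λ(A+F))]/(λA).

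- A = 24, F = 12: 0.788 for a median of 10 months and 0.609 for 17, mean 0.698.
- 164 × 0.698 = 114.5 deaths, consistent with 112.
- 88 deaths would need only 88/0.698, about 126 patients.

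The 164 patients were therefore built on 112 events. The mismatch lies in the alpha or power stated beside that count.

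**Effect on the threshold.** Critical HR = exp(−2 z_alpha/√d).

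| Deaths at analysis | One-sided 0.05 | Two-sided 0.05 |
|---|---|---|
| 112 | 0.733 | 0.690 |
| 128 | 0.748 | 0.707 |
| 151 | 0.765 | 0.727 |

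The last two rows illustrate the extended 45 + 12 month plan under the same medians and assumed uniform accrual. The mean probability of death is 0.793, which gives about 128 deaths from 161.5 patients (190 × 0.85) and 151 from 190.

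**The case against.** One-sided 0.05 is written identically in two sections, and the objective is directional superiority. A reader may fairly say that the declared level is clear and only the power is understated, which harms nobody. Much of this stands. The document does not show whether the alpha or the power was misdeclared. One might infer from the exact match that two-sided 0.05 was certainly intended; the match is strong evidence about how 112 was computed, but the protocol does not say so. Keeping one-sided 0.05 and correcting the power would also make the sentence true. What does not stand is leaving it as it is, since it is false under either intent.

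Three further inferences are tempting and not supported:

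- **That the level could be chosen once the data are seen.** This is conjecture. The protocol names one level, and a statistical analysis plan, not shown here, may fix the test. Such a plan would not correct these two sections.
- **That the 36-month basis in Section 12.1 contradicts the 57 months in Section 0.6.** Section 12.2 explains that enrollment was first planned for 24 months and was extended because it was slow. The 24 + 12 month text is the original calculation, and it reproduces.
- **That the disputed range is always 0.69 to 0.73.** It holds only at 112 deaths and moves with the count, as the second table shows. The 128–151 deaths are themselves rough. Section 12.2 reports 180 of 190 enrolled by August 2013; taking 180 evenly over 35 months and 10 over the next 10 gives about 135–159. Neither range models the untreated patients whom the efficacy set leaves out.

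**Conclusion.** The sentence is wrong as written in both sections. Its alpha, power and event count cannot all be true. At one-sided 0.05, 80% power needs 88–89 events (92–93 by Freedman), or 112 events give about 87–88% power (86% by Freedman). The 112 corresponds to 80% power at two-sided 0.05. This rests on the protocol's own inputs and on standard event formulas under proportional hazards.

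A reader might infer that the trial is too small. It is not: on the stated assumptions, power at 112 events is about 80% or higher by Schoenfeld under either level. The consequence is confined to the success threshold, where the two readings differ by a factor of two in one-sided error rate (5% against 2.5%) and by about 0.04 in critical hazard ratio. The point matters because this is the only level the protocol gives for its primary endpoint.

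**What to change.** Before the final analysis, state one alpha and sidedness for the overall survival test and make Sections 2.6.5 and 12.1 agree with it. Two repairs are open:

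- **(a) Change to two-sided 0.05.** 112 events, 80% power and 164 patients then agree with no change in size. The cost is a stricter threshold than the present text, with a critical hazard ratio of about 0.69 instead of 0.73 if analysed at 112 deaths.
- **(b) Keep one-sided 0.05.** Restate the power at 112 events as about 87–88%, or the events needed for 80% power as 88–89, naming the formula. The cost is an openly declared 5% one-sided error rate for a superiority claim.

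Either is a wording correction in two sections and adds no patients. Optionally, label the 24 + 12 month figures as the original calculation and note that the extended plan should yield more deaths, which shifts the critical hazard ratio accordingly.

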12.2. Enrollment Period and Follow-up Period

Enrollment period: **45 months**, Follow-up period: 12 months

Initially, the study was started in October 2010 with a planned enrollment period of 24 months. However, the actual pace of enrollment was slower than expected, so the enrollment period was extended by one year in January 2012. As of August 2013, 180 patients (94.7%) have enrolled. Many patients have been unable to start the protocol treatment. Therefore, upon consultation with the research group, it was decided to extend the enrollment period, which was to conclude at the end of September 2013, by 9 months to the end of June 2014.

12.3. Subgroup Analysis

Stratified analysis by average and total sorafenib dose will be performed.

Infusion frequency and overall survival will be compared in the arterial infusion group.

Overall survival will also be compared by baseline patient characteristics (hepatic function, age, sex, and tumor markers).

12.4. Interim Analysis

Interim analysis of efficacy will not be performed in this study.

13. ETHICAL CONSIDERATIONS

13.1. Protection of Patients' Rights

All researchers involved in this study will conduct the study in accordance with the Declaration of Helsinki and the Ethical Guidelines for Clinical Studies (415th Notification of the Ministry of Health, Labour and Welfare, 2008).

Relevant website:

<http://www.mhlw.go.jp/general/seido/kousei/i-kenkyu/rinsyo/dl/shishin.pdf>

13.2. Informed Consent

13.2.1. Informed consent discussion

Prior to enrollment, investigators will give an Informed Consent Form approved by the participating institution (either the appended form or a modified version created by the participating institution) directly to the patient along with a thorough verbal explanation of the following items. In this protocol, “approval by the participating institution” means that the matter was reviewed by the advisory body of the institution (institutional review board or ethics committee) and a written letter of approval was sent to the applicant by the director of the participating institution or the chair of the reviewing committee.

1) Explanation of the diagnosis, stage, and expected prognosis

2) That this study is a clinical trial

The difference between a clinical trial and clinical practice

3) Study design and rationale (e.g., significance, number of enrolled patients, need for the study, objective, and treatment assignment)

4) Protocol treatments

Drug names, routes of administration, dose, treatment schedule, duration of the entire protocol treatment, etc.

5) Anticipated effects of the protocol treatment

Prolongation of survival, tumor shrinkage, symptom alleviation, etc.

6) Expected adverse events, complications, and sequelae and measures to be taken if they occur

Explanation of the severity and incidence of expected adverse events (including complications, sequelae, and treatment-related death) and measures to be taken if an event occurs

7) Study-related costs and compensation

Explanation that the study will be similar to routine care in that treatment costs (both for the protocol treatment and treatment for any adverse events) will be covered by health insurance and compensation for illness or injury will be consistent with that awarded in normal clinical practice

8) Alternative treatments

Current typical treatments (including palliative care) and the procedures, effectiveness, and toxicity of standard therapies

Advantages and disadvantages of selecting alternative treatment

9) Potential benefits and potential risks

Explanation of potential benefits and risks of participating in the study

10) Direct access of medical history

Explanation that medical records may be reviewed, for example, that healthcare providers from another institution may directly access medical history records and other such records with the permission of the institution's director to ensure accuracy

11) Declining to consent and withdrawal of consent

That patients are free to decline to participate in this study before participating, are also free to withdraw consent even after providing consent, and that these decisions will not adversely impact their care

12) Protection of patients' rights

That the utmost efforts will be made to keep names and other personal information confidential

13) Freedom to ask questions

Written notification of contact information of not only their assigned investigator but also the site investigator and the study chair (or study coordinator) and explanation that patients are free to ask questions about the study or treatment

13.2.2. Informed consent

A patient's participation in the study will be requested after they have been given an explanation of the study and sufficient time to consider the decision, and it is confirmed that they have a firm understanding of what the study entails. If the patient personally consents to

participate in the study, it will be confirmed that the name of the doctor who conducted the informed consent discussion, the name of the patient giving informed consent, and the date of informed consent are recorded on the appended Informed Consent Form or an informed consent form in a format chosen by the study site.

The informed consent form will be copied two times. One copy will be given to the patient directly and one copy will be retained by the site coordinator. The original will be stored with medical records.

13.3. Protection of Personal Information and Identification of Patients

To protect the privacy of individual patients, enrollment numbers issued on enrollment will be used to identify or refer to enrolled patients. All researchers will make the utmost effort to protect personal information.

13.4. Adherence to the Protocol

Researchers participating in this study will adhere to this protocol as long as it does not infringe on the safety or rights of patients.

13.5. Conflicts of Interest

This study is being conducted with funds from a Health and Labour Science Research Grant. The study has no commercial affiliations with any company.

13.6. Patents

Because the purpose of this study is to benefit all patients with hepatocellular carcinoma and not to pursue profit for the researchers, no patent applications will be made.

13.7. Approval by Institutional Review Boards or Ethics Committees

Before this study is conducted, it will be reviewed and approved by the institutional review board or ethics committee of each participating institution and then approved by institutional directors. On approval by the institutional review board or ethics committee of each participating institution, the approval letter will be faxed to the office. Each participating institution will retain their original approval letter and the study chair will retain a copy.

14. MONITORING AND AUDITS

14.1. Regular Monitoring

Monitoring will consist of central monitoring of data recorded in CRFs collected by the data center. Monitoring by site visits involving checking data against source documents

on-site will not be performed. Regular monitoring reports prepared by the data center will be submitted to the study chair, the study coordinator, and the Data and Safety Monitoring Committee for consideration.

[figure not shown]
14.2. Aspects of the Study to be Monitored

- 1) Enrollment progress
- 2) Eligibility: Patients who are ineligible or may be ineligible
- 3) Whether protocol treatment is in progress or complete and reasons for discontinuation/completion
- 4) Pre-treatment background factors
- 5) Serious adverse events
- 6) Adverse reactions/adverse events
- 7) Protocol deviations
- 8) Overall survival: All eligible patients
- 9) Other aspects of study progress and safety problems

15. SUPPLEMENTARY STUDY

15.1. Overview

15.1.1. Schema

15.1.2. Objective

To identify stratification biomarkers for sorafenib-based treatment for hepatocellular carcinoma.

15.1.3. Subjects

Patients who are enrolled in the main study and have consented to participate in the

translational study

15.1.4. Samples

[figure not shown]
(1) Peripheral blood (3 time points)

A 4-mL sample of peripheral blood will be collected and serum will be separated by centrifugation and stored. The serum will be used as the sample.

Blood samples will be collected at 3 time points: (1) Before treatment (Pre), (2) 1 month after treatment (day 29), and (3) when treatment is discontinued due to PD (no response).

(2) Tumor tissue biopsy specimen (one specimen)

One tumor tissue biopsy specimen will be carefully collected by liver biopsy (ultrasound-guided needle biopsy) to avoid including non-tumor tissue as much as possible. DNA extracted from the tumor tissue will be used as the sample.

15.1.5. Analysis

Serum collected before treatment will be analyzed using an antibody suspension bead array system (Luminex[®] system) or normal ELISA. Serum humoral factors and growth factors related to sorafenib target genes will be quantified, and proteins related to response to treatment will be identified.

Tumor tissue biopsy specimens will be evaluated and changes in the copy number of various genes in tumor tissue will be analyzed by comparative genomic hybridization (CGH). If the DNA sample is sufficient, somatic cell gene mutations in genes such as sorafenib target genes will be detected by semiglobal gene mutation analysis (OncoCarta) or direct sequencing.

15.1.6. Enrollment period

Same as the main study.

15.1.7. Potential benefits

Identification of protein or gene biomarkers that could predict response to standard

sorafenib-based treatment for hepatocellular carcinoma would make a major contribution to the potential treatment options for hepatocellular carcinoma in the future.

15.1.8. Potential risks and discomforts

Peripheral blood samples (total of 12 mL) and a single tumor tissue specimen from normal liver biopsy (ultrasound-guided needle biopsy) will be analyzed in the translational study, and thus risks and discomforts associated with sample collection should be minimal. Risks related to patient rights and privacy are also very low because (1) the study will be conducted with the informed consent of the patient in accordance with the study protocol, (2) personal information will be anonymized and kept under strict control, (3) “genomic information or gene structures/functions possibly inherited by descendants” will not be analyzed, and (4) the genome of normal tissues will not be analyzed.

15.1.10. Study workflow

Consent for the translational study	
Translational study sample number assigned (at patient enrollment)	
Blood collected (1. Pre-treatment, 2. Day 29, 3. PD: serum isolated and stored frozen) Tumor tissue biopsy (pre-treatment, stored frozen)	
Samples sent to Department of Genome Biology, Kindai University Faculty of Medicine Packed frozen with dry ice and sent by frozen delivery service ・Three tubes of serum × 3 (pre, day 29, PD) ・Tumor tissue biopsy × 1	
Samples stored (Department of Genome Biology, Kindai University Faculty of Medicine)	
Serum	Tumor tissue biopsy
Blood angiogenic factors Growth factors (Measured at Kindai)	CGH OncoCarta Sequence (Measured at Kindai)
Analysis of clinical data and measurement data (Kindai and Niigata University)	

15.2. Background

The concept of the angiogenic switch was first proposed by Folkman in the 1970s. He found that when tumors spread to more than 2 mm³ in diameter, their growth is limited by oxygen supply and nutrition, indicating that angiogenesis is required for further growth. This

concept that angiogenesis by the host is required for tumors to grow in size beyond that point led to the idea that inhibiting tumor angiogenesis could be a target for cancer pharmacotherapy. Angiogenesis inhibitors have been proven clinically effective for many types of cancer, and are now becoming increasingly important.

Sorafenib is a multikinase inhibitor that inhibits angiogenic signal transduction, particularly VEGFR and PDGFR. It is generally classified as an angiogenesis inhibitor because this is its main effect. However, it also has a characteristic inhibitory effect on RAF kinase, and thus also inhibits tumor proliferation signal transduction in cancer cells. When investigated as an antitumor drug for hepatocellular carcinoma, sorafenib was demonstrated to improve overall survival in patients with hepatocellular carcinoma in a phase III clinical trial. Therapeutic use of sorafenib as an angiogenesis inhibitor is also widely practiced in Japan.

It is now clear that copy number abnormalities and activating mutations in genes targeted by molecularly targeted cancer drugs are clinically effective biomarkers for those drugs. The importance of these biomarkers is widely recognized due to findings such as the effect of HER2 expression on trastuzumab, the effect of k-ras mutation on anti-EGFR antibody, and the effect of EGFR gene mutations on EGFR tyrosine kinase inhibitors. Specifically, identifying predictors of response to treatment with antineoplastic agents and stratifying treatment is not only advantageous because it reduces healthcare expenses, but also because it offers clear benefits for the patient such as avoiding adverse events from an ineffective drug and time wasted on ineffective treatment. The importance of biomarkers in predicting response to treatment with angiogenesis inhibitors is widely recognized by basic and clinical researchers alike, and is now the subject of much research. Some blood angiogenic proteins such as VEGF, tumor microvessel density, immunohistological assay of tumor angiogenic factors, and SNP of VEGFRs (the target molecules of multi-tyrosine kinase inhibitors) have also been investigated, but no clinically useful biomarker has been identified.

Two approaches were devised for this translational study. The goal of the first approach, which focuses on the effects of sorafenib as an angiogenesis inhibitor, is to measure the serum concentrations of multiple proteins that act as angiogenic factors and identify predictors of response and factors in drug resistance. The goal of the second approach, which focuses on the direct effect of sorafenib on hepatocellular carcinoma, is to analyze changes in cancer cell genome copy numbers and mutations in VEGFR2-like receptor families (e.g., VEGFRs, FGFRs, PDGFRs, and KIT) and BRAF, which are target molecules for sorafenib.

(1) Blood angiogenic factors and growth factors

Various cytokines, chemokines, and growth factors in blood, mainly VEGF, FGF, IL-8, IL-6, and TNF-alpha, are believed to be potent angiogenic factors.¹ Past studies relating to

predictors of response to sorafenib have investigated factors such as blood VEGF and VEGFRs, tumor vessel density, and tumor VEGF expression, but no useful biomarkers have been identified. Therefore, evaluation of the clinical utility of various blood cytokines, chemokines, and growth factors could lead to the identification of new biomarkers that predict response to treatment and resistance to treatment. The antibody suspension bead arrays system (Bio-Rad Laboratories) can assess 30 to 50 cytokines and chemokines at once under the same conditions and its clinical utility for biomarker discovery has been established.^{2,3} Blood cytokines, chemokines, and growth factors other than VEGF can reduce sensitivity to a drug through the phenomenon of escape, and thus would be significant to include in a study investigating potential predictors of response to sorafenib. This research group has previously shown that the pre-treatment serum concentration of various growth factors is a useful noninvasive biomarker of response to molecularly targeted drugs.⁴ Predictors of response to sorafenib will be identified using methods established in that clinical study.

(2) Cancer cell genome copy number variations

Amplifications and losses in copy number that affect the physical size of the cancer cell genome at a chromosomal level can be the essential etiology of many solid cancers and leukemia. However, copy number variations in certain loci seen in examples such as leukemia and brain cancers are known to define the malignancy and prognosis of the tumor. Genome copy number variations of sorafenib target genes in cancer cells may be useful predictors of response to treatment with sorafenib as tumor factors predicting response.

(3) Cancer cell gene mutations

It is widely recognized that activation of target molecules of molecularly targeted drugs through gene mutations can be a predictor of response. Therefore, mutations in VEGFR2-like receptor families (e.g., VEGFRs, FGFRs, PDGFRs, and KIT) and BRAF, which are target molecules for sorafenib, will be analyzed.

